2.2. Description of the study population.

Women with a singleton pregnancy at 12 – 16 weeks of gestation and a history of at least one previous preterm delivery before 34+0 weeks and/or a history of previous cervical surgery attending the reference hospital and who do not fulfil the exclusion criteria the study will be proposed. The patients will be informed of the intended therapeutic effect and possible side effects. If they agree and after obtaining their informed consent, they will be randomised according to either usual management with rescue cerclage placement only when (and as soon as possible) a cervical shortening below 25 mm occurs (=control group) or cervical pessary placement (= pessary group).

Pessaries or cerclage shall be placed up to 37+0 weeks of gestation. In the control group serial cervical length measurements shall be conducted every 4 weeks in order to diagnose cervical shortening as soon as possible.

2.3. Name and description of the device under investigation.

The Arabin cervical pessary, which is CE-certified for preventing SPB (CE 0482 / EN ISO 13485: 2012 + AC:2012 annex III of the council directive 93/42 EEC).

See annex I.

2.4. Statement that testing will be performed according to protocol, GCP and applicable legal requirements.

The Clinical Trial will be conducted following the protocol, the GCP, and all legal requirements.

3. Objective

This study aims to investigate the benefit of a prophylactic cervical pessary treatment in women at high risk of PTB due to a history of at least one previous preterm delivery before 34+0 weeks and/or a history of previous cervical surgery on the children's long-term survival without neurodevelopmental disability.

Hereby, a standardized and validated test called 'Ages and Stages 3rd edition'²⁷ should evaluate the children's neurodevelopment. The test should be conducted by the parents and takes approximately 12 minutes. The questionnaires will be provided by the sponsor.

4. Design

4.1. Specific description of primary and secondary variables.

4.1.1. Primary outcome:

- Children's long-term survival without neurodevelopmental disability

4.1.2. Secondary outcomes:

- Offspring
 - Time to birth
 - Preterm birth before 37 weeks: rate of delivery before 36+6 weeks
 - Preterm birth before 34 weeks: rate of delivery before 33+6 weeks

Confidential

[figure not shown]
[figure not shown]
- Preterm birth before 32 weeks: rate of delivery before 31+6 weeks

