 - Preterm birth before 30 weeks: rate of delivery before 29+6 weeks
 - Preterm birth before 28 weeks: rate of delivery before 27+6 weeks
 - Birth weight: median weight (g) of the newborns at birth
 - Fetal or neonatal death: rate of intrauterine demise or neonatal death during the first 24 hours
 - Neonatal morbidity: rate of major adverse neonatal outcomes before discharge from the hospital
 - Intraventricular Haemorrhage (IVH): grades III-IV
 - Retinopathy of prematurity
 - Respiratory Distress Syndrome (RDS): grades II-IV,
 - Need for ventilation > 72 h
 - Necrotising enterocolitis
 - Proven or suspected sepsis, antibiotics (>5 days)
 - Need (Duration in days) for neonatal special care (NICU)
 - Harm from intervention
- Mother:
- Maternal death
 - Significant maternal adverse events (rate):
 - Heavy bleeding: bleeding that requires a medical intervention
 - Cervical tear: cervical rupture due to the pessary placement
 - Uterine rupture: rupture of the uterus due to contractions or surgery
 - Physical or psychological intolerance to pessary: discomfort or pain due to the pessary that makes daily life uncomfortable (number of cases)
 - Rupture of membranes before 32 weeks: rate of—rupture of amniotic membranes before 31+6 weeks
 - Infection/inflammation
 - Hospitalisation for threatened preterm labour before 32 weeks: requirement of hospitalisation due to preterm contractions that need medical treatment to try to stop them before 31+6 weeks (rate)
 - Mean hospital stay duration: number of days of admittance at the hospital
 - Use of tocolytic treatment: Type of tocolytic, days of treatment, dose

4.2. Description of the trial design.

Open Multicentre International Collaborative Randomized Controlled Trial, in parallel groups, based on intention-to-treat analysis comparing the placement of a prophylactic cervical pessary with usual management in singleton pregnancies at high-risk of PTB due to a history of at least one previous preterm delivery before 34+0 weeks and/or a history of previous cervical surgery.

4.3. Flowchart.

Confidential

4.4. Description of the medical device and the treatment regimen.

The cervical pessary is a vaginal device (silicone ring) that is used to treat pregnant women for preventing spontaneous preterm birth. This device can be easily placed around the uterine cervix without pain (see annex I).

Confidential

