Every center will receive a password and a username in order to access the database for recruitment, randomization and documentation of patient data. Hereby, a personal identification number will be assigned for every patient. Patient names will not appear in the databases.

This database will be supervised and coordinated by PD [name], Bürgerhospital Frankfurt/M. (Webmaster).

4.8. Identification of data to be collected in the case report files (CRF) that should be considered as data source.

Data will be collected in E-CRF, provided by >[name] Wissenschaft, Berlin< on study software "Castor".

4.9. Definition of what is considered to be the end of the study.

The study will be finished after the 3 year-follow up examination of the surviving children focusing on neurodevelopmental disabilities.

5. Selection and withdrawal of subjects

5.1. Inclusion criteria.

- Women with a singleton pregnancy and a history of at least one previous preterm delivery before 34+0 weeks and/or a history of previous cervical surgery
- 12+0 -16+0 weeks of gestation
- Minimal age of 18 years
- Informed consent signature

5.2. Exclusion criteria.

- Major fetal abnormalities (requiring surgery or leading to infant death or severe handicap)
- Cerclage prior to randomisation
- Uterine malformation
- Placenta previa totalis
- Active vaginal bleeding at the moment of randomization
- Spontaneous rupture of membranes at the time of randomization
- Silicone allergy
- Painful regular uterine contractions
- Current participation in another RCT

5.3. Withdrawal criteria.

If a participant may voluntarily withdraw from treatment or if it is necessary to remove the pessary due to the conditions described before, the patients will be followed as usual until delivery (intention-to-treat analysis).

Replacement of patients is not applicable in this trial.

5.4. Rescue treatment criteria.

Regarding the control group, a McDonald cerclage may be indicated if there is a cervical shortening below 25 mm during the follow-up scans according to the current guidelines and expert recommendations¹¹.

6. Treatment of Subjects

6.1. Treatments to be administered.

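### Seven gestational-age limits in Section 4.1.2 stop one day short of their labels, and Section 9.1 times the secondary analysis before discharge-based outcomes can be known (minor; wording)

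*Combined protocol and SAP*

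**What the plan says.** **Cut-offs.** Section 4.1.2 gives each preterm-birth endpoint a label followed by a definition: "Preterm birth before 37 weeks: rate of delivery before 36+6 weeks", "Preterm birth before 34 weeks: rate of delivery before 33+6 weeks", "Preterm birth before 32 weeks: rate of delivery before 31+6 weeks", "Preterm birth before 30 weeks: rate of delivery before 29+6 weeks" and "Preterm birth before 28 weeks: rate of delivery before 27+6 weeks". Two maternal items labelled as before 32 weeks follow the same pattern. Membrane rupture is defined as "rupture of amniotic membranes before 31+6 weeks", and admission for threatened preterm labour carries the same 31+6 limit. Elsewhere the notation differs. The obstetric-history criterion in Section 5.1 is a "history of at least one previous preterm delivery before 34+0 weeks". In Section 9.1 the test table lists birth before 34 weeks, and the interim list gives both maternal items as below 32 weeks.

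**Timing.** Section 9.1 states that the secondary data set will be complete once the last woman has delivered and that its analysis follows directly. It expects no lost secondary data because follow-up for these endpoints ends at birth. Section 4.1.2 nevertheless includes neonatal morbidity up to hospital discharge, ventilation for more than 72 hours, antibiotics for more than 5 days, days in special care, and neonatal death in the first 24 hours.

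**Death.** Section 4.1.2 limits the fetal or neonatal death endpoint to intrauterine demise and death within 24 hours of birth. The morbidity items do not include death. The fetal/neonatal death row of the Section 9.1 test table and the death item in the interim list state no window.

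**The concern.** An analyst who programs the definitions and one who programs the labels would classify an event on the last day of the week differently. The trial is described in Section 2.1 as part of a prospective meta-analysis, where cut-offs should match across studies. The two 32-week maternal items are also interim tests, any one of which can end the trial.

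The timing text, if followed, would produce a secondary report lacking discharge data for infants still in hospital at the last delivery. These are likely to be the sickest infants.

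The death window matters mainly for that early report, which comes about three years before the primary outcome. An infant who dies after 24 hours but before discharge would enter no clearly defined secondary endpoint. Such an infant may also die before a morbidity item can be diagnosed, so morbidity read alone could look better where survival is worse.

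**Working it through.** **Step 1: cut-offs in days.** Gestational age in days is 7 × weeks + days. A label of before W weeks means fewer than 7W days. The written limit is (W−1)+6, that is 7(W−1) + 6 = 7W − 1 days. With *before* read as strictly less than:

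| Endpoint | Label: day below | Written: day below | Last day by label | Last day as written |
|---|---|---|---|---|
| Birth, 37 weeks | 259 | 258 | 36+6 | 36+5 |
| Birth, 34 weeks | 238 | 237 | 33+6 | 33+5 |
| Birth, 32 weeks | 224 | 223 | 31+6 | 31+5 |
| Birth, 30 weeks | 210 | 209 | 29+6 | 29+5 |
| Birth, 28 weeks | 196 | 195 | 27+6 | 27+5 |
| Membrane rupture, 32 weeks | 224 | 223 | 31+6 | 31+5 |
| Threatened-labour admission, 32 weeks | 224 | 223 | 31+6 | 31+5 |

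All seven differ by exactly one day, in the same direction.

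**Step 2: how many births.** The documents give no gestational-age distribution, so this is an illustration for the 37-week limit only; the other six were not computed.

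- Assumption 1: the recurrence risks in Section 2.1, 17.2% after one and 28% after two previous preterm births, apply to all 310 women. Births before 37 weeks: 0.172 × 310 = 53.3 to 0.28 × 310 = 86.8.
- Assumption 2 (no source in the documents): 25% to 50% of these births fall in week 36, spread evenly over its 7 days. Share on 36+6: 0.25/7 = 3.6% to 0.50/7 = 7.1%.
- Births on 36+6, both arms together: 53.3 × 0.25/7 = 1.9 to 86.8 × 0.50/7 = 6.2, so about 2 to 6.

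Women with conisation may differ. Section 2.1 gives only a roughly 5- to 10-fold increase in risk, without a baseline.

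**Step 3: timing, side by side.** No arithmetic is needed.

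| Section 4.1.2 outcome | Earliest it can be complete | Known at the last birth? |
|---|---|---|
| Neonatal death in first 24 hours | 24 hours after birth | No |
| Ventilation > 72 h | after 72 hours | No |
| Antibiotics > 5 days | after 5 days | No |
| Morbidity before discharge | discharge or death | No |
| Days in special care | end of special care | No |

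The visit schedule in Section 7.2 has a postnatal evaluation column with a neonatal examination but no stated time, so it does not settle the matter.

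**Step 4: where a neonatal death between 24 hours and discharge is counted.** It falls outside the death endpoint of 4.1.2 (24-hour limit) and is not among the listed morbidity items. It is counted in the primary outcome (survival to 3 years) and is a serious adverse event under 8.2, with notification under 8.3. The 9.1 test table and the interim death item leave it open, since neither states a window.

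**The case against.** **Cut-offs.** The intended meaning is fairly clear: the labels, Section 9.1 and the eligibility notation agree with one another. The definitions are probably a slip for up to and including 36+6, and so on. If gestational age is held in days, recoding is trivial. Only the 34-week limit has its own row in the test table. All of this stands and keeps the point small, but the wording needs correcting on either reading.

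**Timing.** Section 9.1 says the data are available after the last delivery and sets no database lock. The remark about follow-up ending at birth explains why little loss is expected, and a postnatal examination is scheduled. A reader might infer that the plan closes secondary data collection at birth. The documents do not say that. What stands is narrower: the stated time of completeness and analysis conflicts with the outcome definitions.

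**Death.** A 24-hour window is a choice, not an error. The test table carries no such limit, the interim item most naturally means any death known at the look, and the harm-from-intervention outcome is undefined. The extracted layout also does not show whether the morbidity list is exhaustive. A reader might infer that later neonatal deaths are lost to the trial. They are not: the primary outcome and safety reporting both capture them. A reader might also infer that the unstated window could readily change an interim stopping decision. The documents give no mortality rate or timing of deaths to support this, and the rule stops on any one of several tests, so a different result on the death item alone need not change the outcome.

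**Conclusion.** Minor overall, in three parts of different standing.

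- **Cut-offs: wrong as written, small.** All seven definitions end one day before their labels. This is certain if *before* is strict. The estimate of about 2 to 6 births rests wholly on the two assumptions in the working. The rule applies to both arms alike, and nothing in the documents suggests that it favours either.
- **Timing: wrong as written.** At least five outcome elements cannot be known at the last delivery. The number of infants affected depends on how many are still in hospital then, which the documents do not allow to be estimated.
- **Death window: an improvement, not a correction.** The gain is a clearer early secondary report and an interim item defined before data are seen. Its size is unknown.

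**What to change.** 1. **Section 4.1.2, cut-offs.** Write the five preterm-birth limits as before 37+0, 34+0, 32+0, 30+0 and 28+0, and both maternal limits as before 32+0. Cost: wording only.
2. **Section 9.1, timing.** State that the secondary analysis runs once the last infant has been discharged or has died, or at a maximum wait fixed in advance, whichever comes first. Report infants still in hospital at that point by arm. Replace the statement that follow-up ends at birth. Cost: a short delay, which the morbidity endpoint already requires; the cap prevents one long stay from holding up the whole report.
3. **Sections 4.1.2 and 9.1, death (optional).** Count intrauterine demise and neonatal death up to discharge. Report death or major morbidity before discharge beside its components. State that the interim death item counts all fetal and neonatal deaths known at a cut-off date set in advance after the 150th birth. The safety look need not wait for discharges, but infants still in hospital will have shorter follow-up, so give their number by arm.

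The documents list no eCRF fields. The sponsor should confirm that gestational age in days and the dates of discharge and death are recorded.

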Women with a singleton pregnancy at 12+0 – 16+0 weeks of gestation and a history of at least one previous preterm delivery before 34+0 weeks and/or a history of previous cervical surgery attending the reference hospital for a preventive examination will be informed of the ongoing trial. The patient will be advised of the intended therapeutic effect and possible side effects. If they agree and after obtaining their informed consent, they will be randomised according to either usual management (=control group) or cervical pessary placement up to 37+0 weeks (=pessary group).

If the pregnant woman is assigned to the pessary group and after having excluded a vaginal infection the pessary will be inserted directly. This procedure does not need anaesthesia and it does not need to be done in a surgery room. After the insertion of the pessary the correct fit of the pessary is verified by transvaginal ultrasound and in case it does not fit perfectly, it can easily be adjusted.

In the control-group the cervical length of the women will be evaluated by transvaginal ultrasound scan started from randomization and every 4 weeks; if a cervical shortening below 25mm is detected a Mc Donald cerclage will be placed.

The pessary will be removed at 37+0 weeks of gestation, or before if any unexpected event occurs (see 4.6). After insertion of the pessary the obstetrical management during the remainder of the pregnancy will be usual management.

Further surveillance of the pregnancy will not be influenced by the participation on the study.

4.5. Expected duration of subject's participation.

Starting recruitment: June, 1st, 2018

Finishing recruitment and follow-up: est. June 1st, 2023.

Final report: Sept. 1st, 2023

4.6. Completion and interruption criteria of the study or the subjects.

The pessary will be removed at 37+0 weeks of pregnancy. The indications to remove them before this time will be: active bleeding stronger than period bleeding, persistent contractions after tocolysis and premature rupture of the membranes after 34+0 weeks.

After removing the pessary, the obstetrical management will be done as usual and will not be influenced by the study.

4.7. Maintenance of the randomisation codes and test procedures of the trial.

Every participating centre will have its own randomisation list.

We have created a database in a website so it can be accessed worldwide, that every hospital will be able to randomize their patients.

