To ensure no confusion or misunderstanding of the difference between the terms "serious" and "severe", which are not synonymous, the following note of clarification is provided:

The term "severe" is often used to describe the intensity (severity) of a specific event (as in mild, moderate, or severe myocardial infarction); the event itself, however, may be of relatively minor medical significance (such as severe headache). This is not the same as "serious," which is based on patient/event outcome or action criteria usually associated with events that pose a threat to a participant's life or functioning as defined in the bullet points above. Seriousness (not severity) serves as a guide for defining regulatory reporting obligations.

Serious Adverse Reaction (SAR): An adverse event (expected or unexpected) that is both serious and, in the opinion of the reporting investigator, believed with reasonable probability to be due to one of the study treatments, based on the information provided.

Suspected Unexpected Serious Adverse Reaction: A serious adverse reaction, the nature or severity of which is not consistent with the applicable product information

Confidential

(e.g. Investigator's Brochure for an unapproved investigational product or summary of product characteristics for an approved product).

8.3. Procedures for immediate notification of serious or unexpected adverse events.

All AEs occurring during the study /or observed by the investigator or reported by the participant, whether or not attributed to study medication, will be recorded on the CRF. The following information will be recorded: description, date of onset and end date, severity, and assessment of relatedness to study medication, other suspect drug or device and action taken. Follow-up information should be provided as necessary.

AEs considered related to the sanitary device, as judged by a medically qualified investigator, will be followed until resolution or the event is considered stable. All related AEs that result in a participant's withdrawal from the study or are present at the end of the study, should be followed up until a satisfactory resolution occurs.

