It will be left to the investigator's clinical judgment whether or not an AE is of sufficient severity to require the participant's removal from treatment. A participant may also voluntarily withdraw from treatment due to what he or she perceives as an intolerable AE. If either of these occurs, the participant must undergo an end of study assessment and be given appropriate care under medical supervision until symptoms cease or the condition becomes stable.

A medically qualified investigator will assess the relationship of AEs to the study medication.

All SAEs must be reported to the main investigator. He will perform an initial check of the report, request any additional information, and he will notify it to the Ethics Committee. All SAE information will be recorded. It may be appropriate that some SAEs do not require immediate reporting but this must be justified. Justification might be determined, for example, by admission to hospital, or prolongation of hospitalization, where this is to be expected in the underlying disease or condition.

All adverse events (AE) life-threatening or resulting in death will be notified within 24 hours. All AE that are not life-threatening will be notified within 15 days. The rest of AE will be recorded and analyzed at the end of the study.

9. Statistics

9.1. Description of statistical methods.

A descriptive analysis by preterm birth will be carried out calculating means and medians for quantitative variables and proportions for categorical variables.

The primary statistical aim is to compare the primary combined outcome "long-term survival without neuro-developmental disability at 3 years follow up" between the two treatment groups with a two-sided chi-square test. In general, statistical comparisons will be two-sided and use appropriate tests according to the scale of the outcome. A multivariate logistic regression will be fitted to control for possible confounders. Relative risks and 95% confidence interval as well as adjusted odds ratios will be calculated for the binary outcomes. Statistical significance will be accepted in all cases with a $p \leq 0.05$.

The main statistical evaluation will be performed at two time points.

(1) The complete data set for the secondary endpoints will be available after the last women enrolled in this study has delivered her neonate, so the analysis of these outcome parameter will be done right after this event.

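### Two secondary outcome definitions give incomplete or one-sided comparisons: neonatal death stops at 24 hours, and cervical tear counts only rupture caused by the pessary

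*Combined protocol and SAP*

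**What the plan says.** Section 4.1.2 lists the secondary outcomes with short definitions. Four of them matter here.

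- The death outcome is given as "rate of intrauterine demise or neonatal death during the first 24 hours", with no later window.
- For morbidity of the newborn, the definition reads "rate of major adverse neonatal outcomes before discharge from the hospital". The listed components are haemorrhage, retinopathy, respiratory distress, ventilation, enterocolitis and sepsis. Death is not among them.
- Under significant maternal adverse events: "Cervical tear: cervical rupture due to the pessary placement".
- Under the same heading: "Heavy bleeding: bleeding that requires a medical intervention".

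The control strategy includes a procedure on the cervix. Section 4.4 says "if a cervical shortening below 25mm is detected a Mc Donald cerclage will be placed"; section 5.4 says "a McDonald cerclage may be indicated if there is a cervical shortening below 25 mm".

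The table of tests in section 9.1 has a row for fetal/neonatal death and a row for maternal adverse events, each with a chi-square or Fisher test. Neither row changes the definitions, and cervical tear has no row of its own. Section 9.1 places the secondary analysis directly after the last delivery and the primary analysis three years later. Its interim safety list includes death without a time window.

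Section 8.3 provides separate capture. Adverse events, "whether or not attributed to study medication, will be recorded on the CRF", and for the gravest ones, "All adverse events (AE) life-threatening or resulting in death will be notified within 24 hours".

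**The concern.** A baby who dies on day 3 is not an event in the death row. Such a baby enters the morbidity row only if a listed complication was also recorded. The secondary report comes about three years before the primary one and would carry a death row whose short label does not show the limit.

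The tear item has a different fault. Both arms can undergo a procedure on the cervix, but the definition recognises injury from only one of them. The item can show harm from the pessary and cannot show harm from cerclage. The comparison may therefore read against the pessary, or conceal an advantage of the pessary over cerclage.

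**Working it through.** There is no figure in the plan to reproduce: the documents give no death or tear rate. The wording settles both points, and the arithmetic only sizes them. It uses 155 women per arm (section 9.2), a two-sided Fisher test at 5% and exact enumeration. All rates below are assumptions.

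**1. Death: where a later death is counted**

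| Place | Neonatal death after 24 hours, before discharge |
|---|---|
| Fetal or neonatal death (4.1.2) | Not counted |
| Neonatal morbidity (4.1.2) | Not counted as a death |
| Harm from intervention (4.1.2) | Undefined |
| Interim death item (9.1) | Unclear, no window given |
| Serious adverse events (8.2, 8.3) | Counted |
| 3-year primary outcome | Counted |

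**2. Death: size**

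Assume half of all deaths are neonatal and a share L of those occurs after 24 hours. Deaths lost = 155 × (sum of the two rates) × 0.5 × L. Each arm's rate is multiplied by 1 − 0.5L.

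| Assumed rates, pessary vs control | Deaths | L | Lost | Power |
|---|---|---|---|---|
| 4% vs 8% | 155 × 0.12 = 18.6 | 0 | 0 | 0.234 |
| | | 30% | 2.8 | 0.189 |
| | | 70% | 6.5 | 0.131 |
| 2% vs 6% | 155 × 0.08 = 12.4 | 0 | 0 | 0.318 |
| | | 30% | 1.9 | 0.256 |
| | | 70% | 4.3 | 0.171 |

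With a neonatal share of 30-70% instead of half, power under the limit runs from 0.095 to 0.281. The comparison is weak with either window. L is taken as equal in both arms, so these figures show lost events and no bias.

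**3. Tear tested as its own item**

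The control count is zero by definition, apart from crossover. Against 0 of 155, five pessary tears give p = 0.060 and six give p = 0.030, however many cerclage tears occurred. If the true rates are equal, the chance of a significant result against the pessary is:

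| True tear rate in each arm | As written | Both arms counted |
|---|---|---|
| 0.5% | 0.0001 | 0.0001 |
| 1% | 0.005 | 0.001 |

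**4. Tear inside a maternal adverse-event composite**

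Assume other events in 5% of each arm, a true tear rate t in both arms, and a share o of cerclage tears already scored as heavy bleeding.

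- Pessary rate = 1 − 0.95(1 − t). At t = 1% this is 1 − 0.95 × 0.99 = 5.95%.
- Control rate as written = 1 − 0.95(1 − o·t). At o = 0 this is 5.00%; at o = 0.5 it is 1 − 0.95 × 0.995 = 5.475%.
- Relative risk: 5.95/5.00 = 1.19 (o = 0) or 5.95/5.475 = 1.09 (o = 0.5). With both arms counted it is 1.0.
- Chance of false significance against the pessary: 3.1% or 2.1%, against 1.4% with both arms counted.

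At t = 0.2% the relative risk is 1.04 or 1.02.

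**5. Related wording**

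Each preterm cut-off is one day short of its label: birth before 37 weeks is written as before 36+6, and likewise at 34, 32, 30 and 28 weeks and for the two maternal 32-week items. If 4-8% of women deliver in week 36 (assumption), one day is 4%/7 = 0.57 to 8%/7 = 1.14 percentage points, or 0.9 to 1.8 of 155 women per arm, equally in both arms. Section 9.1 also calls the secondary data complete at the last delivery, although morbidity is followed to discharge.

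**The case against.** **Later deaths are not lost to the trial.** This stands. They are reportable as serious adverse events and count in the primary outcome. A reader might infer that the 24-hour limit biases the trial or weakens its interim safety review. The documents support neither: no difference between arms in the timing of death is given, and the interim death item has no window.

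**The tear effect needs implausible rates.** This largely stands. Equal tear rates of 2% or 3% would raise the item-level chance of a false finding to 9% or 32%, and a reader might take these as the size of the problem. But only controls whose cervix shortens receive a cerclage. If that is 10-33% of controls (assumption; uptake is not stated), a 3% rate over all controls means 0.03/0.33 = 9% to 0.03/0.10 = 30% of cerclages tearing. Even 1% means 3-10%. The small-rate figures are the ones to rely on.

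**There is no separate tear test.** This stands in part. The table of tests names only maternal adverse events, and the heading in section 4.1.2 speaks of a rate, which favours a composite. The plan does not say so outright, and the composite inherits the one-sided component. Cervical tear is also not named in the interim list.

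**A device-specific harm item can be legitimate.** This is true, and intolerance to the pessary is such an item. That outcome can arise only with a pessary, and its label says so. Cervical tear has a neutral label, sits in a between-arm rate, and can also follow the control arm's procedure.

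**Adverse-event recording already captures cerclage tears.** They may be recorded, and those needing intervention for bleeding may count as heavy bleeding. Neither makes them tear events in the comparison.

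**Conclusion.** The point holds as a limited correction that should be made. As written, the death row omits later in-hospital deaths, and controls cannot score on cervical tear apart from crossover. Both conclusions follow from the wording and need no assumed rate.

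The size does rest on assumptions. For death, about 2 to 6.5 of 12 to 19 deaths would be left out if half of deaths are neonatal and 30-70% of those are late. This is a gap in completeness without a shown direction. For tear, the direction is against the pessary, and at equal rates of 1% or less the effect is small: at most 0.5% false significance for the item, and a composite relative risk of 1.09-1.19 at 1% with 5% other events. It would be wrong to infer that the primary outcome, the sample size or adverse-event capture is compromised; none of them depends on these definitions.

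**What to change.** - Define fetal or neonatal death as intrauterine death or neonatal death before hospital discharge, matching the morbidity item, and state that the interim death item uses the same definition.
- Count cervical tear in both arms by one rule regardless of device. Record cause and timing (pessary, cerclage, delivery) so that device-related tears can be reported separately.
- State whether maternal adverse events are tested as a composite or item by item.
- Consequential edits: write the cut-offs as before 37+0, 34+0, 32+0, 30+0 and 28+0, and before 32+0 for membrane rupture and hospitalisation. Lock the secondary data after the last neonate is discharged.

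The cost is small: vital status at discharge, and cause and timing for each tear. The case report form is not in the documents, so the number of new fields is unknown, but morbidity is already followed to discharge and adverse events are already recorded.

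There are three downsides. The secondary report comes slightly later. A window to discharge varies with length of stay, which may differ by arm; a 28-day window would be fixed but may need an extra contact for babies discharged earlier. Counting every tear admits delivery tears unrelated to either device, which dilutes the device signal; recording the cause only partly offsets this.
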